3.3. Study Definitions and Derived Variables

Medically significant wheezing is defined as wheezing on physical exam, signs of respiratory distress (tachypnea, retractions, or dyspnea), hypoxemia (O_2 saturation < 95%), or new bronchodilator prescription, or use of daily bronchodilator therapy (not on an “as needed “basis) from receipt of the first vaccination through 3 months after the first vaccination. Wheezing experienced after first vaccination through Visit 02 is considered a solicited event. Wheezing recorded after Visit 02 is considered an AESI. For all wheezing events the following will be recorded: whether wheezing is diffuse or localized, respiratory rate, oxygen saturation, medications associated with wheezing, and physician’s description on auscultation.

For laboratory and immunogenicity measures the baseline value will be defined as the last value obtained prior to the first vaccination/dose of study product.

Individual Hemagglutination inhibition (HAI) and neutralization results will be reported as a titer with values of 10×2^k , where $k=0, 1, 2$, etc. The lower limit of detection for the HAI and neutralization assays is 1:10; values below the limit of detection will be reported as ‘<10’. Values used in analysis will be imputed as one-half the limit of detection ($10/2 = 5$). For analysis, the geometric mean of repeated HAI or neutralization results will for each subject and visit will be computed and used as the response for all subsequent calculations.

Individual nasal sIgA results will be reported as a titer with values of 2^k where $k=0, 1, 2$, etc. The lower limit of detection for the nasal sIgA results is 2; values below the limit of detection will be reported as <2. Values used in analysis will be imputed as one-half the limit of detection ($2/2 = 1$). For analysis, the geometric mean of repeated sIgA results for each subject and visit will be computed and used as the response for all subsequent calculations. Relative (normalized) strain-specific sIgA results will be calculated by dividing the strain-specific value by total sIgA at each time point for each subject.

The lower limit of detection for the frequency of conserved internal viral protein-specific IFN- γ T cells per million peripheral blood mononuclear cells (PBMC) as measured by ELISPOT assay is 0.

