4.5.1. Immunogenicity Variables

Individual HAI and Neut titer results will be reported by the laboratory at St. Louis University for the H3N2 M2SR-like (A/Brisbane/10/2007) and H3N2 QIV-like viruses (A/Singapore/INFIMH-16-0019/2016 and cell culture-propagated A/North Carolina/04/2016 for 2018/2019 and any additional strains specific to the 2019/2020 QIV). The HAI assay for the A/North Carolina/04/2016 strain only will be tested using both turkey and guinea pig red blood cells (RBC) separately, both with and without oseltamivir. All other strains will be tested using turkey RBC without oseltamivir, and these results from these conditions will be used in grouped displays of QIV-like results. For analysis, the geometric mean (calculated on natural log scale) of repeated results for each subject at each visit will be computed and used as the response for all subsequent calculations. The variation arising from multiple measurements for an individual at a single time point is not used in subsequent calculations. See [Section 3.3](#) for definitions of derived variables for the analysis of HAI and Neut data.

The laboratory at Saint Louis University will also provide individual titer results for nasal sIgA against the H3N2 M2SR-like and H3N2 QIV-like viruses and total sIgA, as well as individual H3 HA-specific (H3 M2SR-like and QIV-like viruses) For analysis, the geometric mean (calculated on natural log scale) of repeated results for each subject at each visit will be computed and used as the response for all subsequent calculations. The variation arising from multiple measurements for an individual at a single time point is not used in subsequent calculations. The frequency of conserved internal viral protein-specific (H3 M2SR-like and QIV-like viruses) IFN- γ T Cells per million PBMC as measured by ELISPOT will also be reported. See Section 3.3 for definitions of derived variables for the analysis of sIgA and IFN- γ T Cell results.

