8. IMMUNOGENICITY EVALUATION

This study was not designed to test a specific null hypothesis, rather the objective was to obtain preliminary estimates of immune response to the M2SR vaccine alone and after subsequent receipt of licensed seasonal QIV. Immunogenicity data summaries and analysis for secondary endpoints will be presented for the ITT and PP populations.

Immune responses for the M2SR strain (A/Brisbane/10/2007 (H3N2)) will be summarized at each time point presented overall and stratified by study arm. Immune responses for each QIV strain (egg-based A/Singapore/INFIMH-16-0019/2016 and cell culture-propagated A/North Carolina/04/2016 and any additional strains specific to the 2019/2020 QIV vaccine) will be summarized at each time point presented by stratified by study arm for each season and H3N2 QIV response overall. Descriptive summary statistics will be provided for all assays, strains, and time points.

HAI and MN serum antibody titer summaries will include GMT, the proportion of subjects with a titer $\geq 1:40$, GMFR, and the proportion of subjects achieving seroconversion along with corresponding 95% confidence intervals for each measure. Exact (Blaker) confidence intervals will be presented for proportional endpoints [3]. Summaries of HAI and MN responses are presented in [Table 20](#), [Table 21](#), [Table 22](#), [Table 23](#), [Table 24](#), [Table 25](#), [Table 26](#), [Table 27](#), [Table 28](#), and [Table 29](#).

For nasal sIgA responses, the GMT with corresponding 95% CI visits strain-specific and relative sIgA (relative sIgA = strain-specific sIgA / total sIgA) results will be reported for the M2SR and QIV A/H3N2 strains. For post-baseline visits GMFR with corresponding 95% CI will also be calculated, as well as the proportion of subjects with ≥ 2 -fold and ≥ 4 -fold rise with corresponding 95% CI. Differences in GMT and GMFR between study groups will be presented at each time point. For QIV-like strains, differences will be calculated between overall response to the year-matched QIV strains. Summaries of nasal sIgA responses are presented in [Table 30](#), [Table 31](#), [Table 32](#), and [Table 33](#).

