Tables with similar format:

Table 27: Summaries of Hemagglutination Inhibition Antibody Against H3N2 QIV-like Virus by Time Point and Study Group - PP Population

Table 28: Summaries of Neutralizing Antibody Against H3N2 QIV-like Virus by Time Point and Study Group - mITT Population*

[Implementation Note: This table will be repeated for both the strain A/Singapore/INFIMH-16-0019/2016 (grown in eggs and missing HA glycosylation site) and A/NorthCarolina/04/2016 (grown only in cell lines and retains HA glycosylation site. Only results for the A/NorthCarolina/04/2016 tested using Turkey RBC will be generated for the interim report.]

Table 29: Summaries of Neutralizing Antibody Against H3N2 QIV-like Virus by Time Point and Study Group - PP Population

Table 30: Summaries of Nasal sIgA Against M2SR-like H3 HA by Time Point and Study Group - mITT Population

Time Point	Statistic	Without Normalization		Normalized	
		M2SR (N=X)	Placebo (N=X)	M2SR (N=X)	Placebo (N=X)
Baseline	n	x	x	x	x
	GMT (95% CI)	x.x (x.x,x.x)	x.x (x.x,x.x)	x.x (x.x,x.x)	x.x (x.x,x.x)
Day 8	n	x	x	x	x
	GMT (95% CI)	x.x (x.x,x.x)	x.x (x.x,x.x)	x.x (x.x,x.x)	x.x (x.x,x.x)
	GMFR (95% CI)	x.x (x.x,x.x)	x.x (x.x,x.x)	x.x (x.x,x.x)	x.x (x.x,x.x)
	Any Fold Rise - % (95% CI)	xx (xx.x,xx.x)	xx (xx.x,xx.x)	xx (xx.x,xx.x)	xx (xx.x,xx.x)
	2-Fold Rise - % (95% CI)	xx (xx.x,xx.x)	xx (xx.x,xx.x)	xx (xx.x,xx.x)	xx (xx.x,xx.x)
	4-Fold Rise - % (95% CI)	xx (xx.x,xx.x)	xx (xx.x,xx.x)	xx (xx.x,xx.x)	xx (xx.x,xx.x)
Day 22	n	x	x	x	x
	GMT (95% CI)	x.x (x.x,x.x)	x.x (x.x,x.x)	x.x (x.x,x.x)	x.x (x.x,x.x)
	GMFR (95% CI)	x.x (x.x,x.x)	x.x (x.x,x.x)	x.x (x.x,x.x)	x.x (x.x,x.x)
	Any Fold Rise - % (95% CI)	xx (xx.x,xx.x)	xx (xx.x,xx.x)	xx (xx.x,xx.x)	xx (xx.x,xx.x)
	2-Fold Rise - % (95% CI)	xx (xx.x,xx.x)	xx (xx.x,xx.x)	xx (xx.x,xx.x)	xx (xx.x,xx.x)
	4-Fold Rise - % (95% CI)	xx (xx.x,xx.x)	xx (xx.x,xx.x)	xx (xx.x,xx.x)	xx (xx.x,xx.x)
Day 57	n	x	x	x	x
	GMT (95% CI)	x.x (x.x,x.x)	x.x (x.x,x.x)	x.x (x.x,x.x)	x.x (x.x,x.x)
	GMFR (95% CI)	x.x (x.x,x.x)	x.x (x.x,x.x)	x.x (x.x,x.x)	x.x (x.x,x.x)
	Any Fold Rise - % (95% CI)	xx (xx.x,xx.x)	xx (xx.x,xx.x)	xx (xx.x,xx.x)	xx (xx.x,xx.x)
	2-Fold Rise - % (95% CI)	xx (xx.x,xx.x)	xx (xx.x,xx.x)	xx (xx.x,xx.x)	xx (xx.x,xx.x)
	4-Fold Rise - % (95% CI)	xx (xx.x,xx.x)	xx (xx.x,xx.x)	xx (xx.x,xx.x)	xx (xx.x,xx.x)
Day 92	n	x	x	x	x
	GMT (95% CI)	x.x (x.x,x.x)	x.x (x.x,x.x)	x.x (x.x,x.x)	x.x (x.x,x.x)
	GMFR (95% CI)	x.x (x.x,x.x)	x.x (x.x,x.x)	x.x (x.x,x.x)	x.x (x.x,x.x)

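### Normalized sIgA can score a child with no detectable strain-specific antibody as a 2-fold or 4-fold responder, because the half-limit value is divided by a changing total sIgA

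*SAP*

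**What the plan says.** SAP 3.3 puts nasal sIgA on a 2-fold scale ("Individual nasal sIgA results will be reported as a titer with values of" 2 to the power k) with a lower limit of detection of 2. Below that limit, "values below the limit of detection will be reported as <2. Values used in analysis will be imputed as one-half the limit of detection", which is 2/2 = 1. Replicates are then combined: "the geometric mean of repeated sIgA results for each subject and visit will be computed and used as the response for all subsequent calculations". The ratio is therefore formed after the substitution: "Relative (normalized) strain-specific sIgA results will be calculated by dividing the strain-specific value by total sIgA at each time point for each subject". SAP 4.5.1 says the laboratory supplies "individual titer results for nasal sIgA against the H3N2 M2SR-like and H3N2 QIV-like viruses and total sIgA", so the denominator is also a titer.

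SAP 8 repeats the definition ("relative sIgA = strain-specific sIgA / total sIgA") and plans GMT, GMFR and the proportions with at least a 2-fold and at least a 4-fold rise. The shells of Tables 30 and 32 carry these rows in both the unnormalized and the normalized columns and add a third, "Any Fold Rise - % (95% CI)". Tables 31 and 33 use the same layout for the per-protocol population. The secondary endpoint itself (Protocol 3.2.2, SAP 3.2.2) is GMT and GMFR of nasal sIgA, with and without normalization.

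Neither document requires a detectable strain-specific result before a normalized rise is counted, sets a minimum total sIgA, or plans a sensitivity analysis for values below the limit. SAP 6.5 deals with missing values and outliers, not with results below detection.

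**The concern.** Normalization is meant to remove differences in how much secretion each swab recovered. That works when numerator and denominator both scale with recovery. A numerator held at 1 does not scale. For a child below the limit at both visits, the normalized fold rise contains no measurement of strain-specific antibody; it is the inverse change in total sIgA. A more dilute second swab, or any other fall in total sIgA, then looks like a mucosal response.

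Mucosal antibody is a secondary objective, and the normalized result is one of its two prespecified forms. With about 25 children per arm, each false responder moves an arm's rate by 4 percentage points. If false responders appear in both arms, both proportions are too high and the contrast between M2SR and placebo is blurred.

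**Working it through.** **Inputs.** Detection limit 2, substituted value 1, ratio to same-visit total sIgA, and baseline as the last value before the first vaccination (all SAP 3.3). Rises of at least 2-fold and 4-fold (SAP 8); the any-rise row (Tables 30 and 32). About 25 children per arm (SAP 5). The documents give no SD for total sIgA and no share of undetectable samples.

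**The plan's own figure.** 2/2 = 1, as SAP 3.3 states.

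**Formula.** Let S be strain-specific and T total sIgA, with 0 for baseline and 1 for post-dose. The normalized fold rise is (S1/T1)/(S0/T0) = (S1/S0) × (T0/T1). With S0 = S1 = 1 it reduces to T0/T1.

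**Worked cases.**

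| Strain-specific | Total sIgA | Unnormalized fold | Normalized fold |
|---|---|---|---|
| <2 to <2 | 256 to 128 | 1.0 | 2.0 |
| <2 to <2 | 256 to 64 | 1.0 | 4.0 |
| <2 to <2 | 256 to 1024 | 1.0 | 0.25 |
| 2 to <2 | 256 to 64 | 0.5 | 2.0 |
| 16 to 4 | 256 to 64 | 0.25 | 1.0 |
| 16 to 16 | 256 to 64 | 1.0 | 4.0 |

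In rows 1 and 2, one 2-fold step down in total sIgA meets the 2-fold criterion and two steps meet the 4-fold criterion. Row 3 is the mirror image, a false fall. In row 4, a child whose titer became undetectable is scored as a 2-fold responder. Rows 5 and 6 show normalization working as intended above the limit: a pure 4-fold dilution gives 1.0, and a titer held steady in a more dilute swab is a legitimate normalized rise. The fault is confined to substituted values.

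**Rates among children undetectable at both visits, with no true response.** Assume that log2 total sIgA varies between visits within a child with per-visit SD s. The log2 change then has SD s√2. On a continuous scale, P(at least 2-fold) = P(Z ≥ 1/(s√2)) and P(at least 4-fold) = P(Z ≥ 2/(s√2)). For s = 1.0 these are P(Z ≥ 0.707) = 24% and P(Z ≥ 1.414) = 7.9%. If each total is a single reading rounded down to a 2-fold grid, simulation gives higher rates.

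| Per-visit SD (log2) | 2-fold, continuous | 2-fold, grid | 4-fold, continuous | 4-fold, grid |
|---|---|---|---|---|
| 0.5 | 8% | 26% | 0.2% | 2.4% |
| 1.0 | 24% | 36% | 8% | 15% |
| 1.5 | 32% | 41% | 17% | 24% |

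For the any-rise row, symmetry gives 50% on the continuous scale whatever the SD. On the grid, the any-rise rate equals the 2-fold rate.

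**Scale per arm, by assumption only.** If half of an arm (12.5 of 25) were undetectable at both visits and s = 1.0, the expected number of false 4-fold responders per visit is 12.5 × 0.079 = 1.0 (continuous) to 12.5 × 0.149 = 1.9 (grid). With 5 such children it is 0.4 to 0.7; with 20, 1.6 to 3.0.

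**GMFR.** For these pairs the log2 fold is log2 T0 minus log2 T1. Its mean is zero when total sIgA has the same distribution at both visits. The contribution is noise, not a false rise, unless total sIgA shifts differently by arm.

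**The case against.** The strongest case against is that the prespecified endpoint is GMT and GMFR, where the error is centred on zero. The rise proportions are additional descriptive rows, and the any-rise row appears only in the shells. The study tests no formal hypothesis. The unnormalized columns sit alongside, and Listing 9 prints both forms per child and visit, so an attentive reader could find the discrepancy. All of that stands. It limits the harm, but the normalized proportions would still be wrong as printed.

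The rates are also fragile. They apply only to children undetectable at both visits, a share the documents do not give. They also depend on the grid: because the analysed value is the geometric mean of replicates, it need not lie on a 2-fold step, and at an SD of 0.5 the grid raises the 4-fold rate about tenfold. This is why both scales are shown.

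A reader might infer three stronger claims, which the documents do not support:

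- **Bias towards M2SR.** Runny nose is a solicited reaction, so secretions might be more dilute in that arm. But it is solicited in both arms, Protocol 2.3.1 says saline may itself cause mild rhinitis, solicited collection stops at about Day 8, and nothing links rhinorrhea to total sIgA in the swab. An arm difference at Day 8 cannot be excluded, but it is not shown.
- **Accumulation over the five post-baseline visits.** Tables 30-33 report each visit separately; no planned table counts a child as a responder at any visit.
- **A wrong decision on the exploratory anti-NA IgA assays.** SAP 8.3 leaves that to the judgment of the scientific lead and principal investigator on M2SR-matched sIgA GMFR. It does not say that the normalized form is used, and it does not use rise proportions.

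**Conclusion.** The concern holds as a classification error built into a stated rule. Under SAP 3.3, SAP 8 and Tables 30-33 as written, a child undetectable at both visits is scored on total sIgA alone, and a child who goes from 2 to undetectable can also score a rise. Among children undetectable at both visits the error can only add responders to the proportions; in GMFR it adds noise centred on zero unless dilution differs by arm.

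How many children this would affect cannot be determined from the documents. The per-visit false 4-fold rate runs from about 0.2% to 24% across the assumed SDs and the two scales, and the false 2-fold rate from about 8% to 41%, both conditional on being undetectable twice. If few children are below the limit, the effect is negligible; if many are, it could amount to a few false responders per arm at a visit. The rule should be corrected because the correction is cheap and best settled before unblinding, not because a large bias has been demonstrated.

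**What to change.** In SAP 3.3 and as a footnote to Tables 30-33, count a normalized any, 2-fold or 4-fold rise only when the post-dose strain-specific titer is detectable (2 or higher). Children undetectable post-dose are then non-responders, which resolves both the <2 to <2 and the 2 to <2 cases. Do not also require the raw titer to exceed its baseline value: that would discard legitimate normalized rises above the limit, such as 16/256 to 16/64.

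Report, per arm and visit, the number of pairs undetectable at both visits. Keep the planned normalized GMFR and add, as a sensitivity analysis, the same GMFR with those pairs set to a fold of 1. That value is a convention, which is why the count should accompany it.

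The cost is one SAP sentence, a footnote, a count row and one extra GMFR row, with no new samples or assays. The downside is small: a true rise hidden below detection by a dilute swab counts as non-response, as it already does in the unnormalized column.

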6. GENERAL STATISTICAL CONSIDERATIONS

6.1. General Principles

Unless otherwise specified, continuous variables will be summarized using the following descriptive statistics: n (non-missing sample size), mean, standard deviation, median, maximum and minimum. For post-baseline visits, fold rise from baseline will be calculated. Unless otherwise specified, confidence intervals for means (arithmetic or geometric) will be calculated using the student's t distribution with confidence level $\alpha=0.05$ (95% confidence). P-values for spearman correlations will be calculated using the student's t distribution testing the hypothesis that the two variables tested are not correlated. The frequency and percentages (based on the non-missing sample size) of observed levels will be reported for all categorical measures. In general, all data will be listed, sorted by site, study group and subject, and when appropriate by visit number within subject. All summary tables will be structured with a column for each study group in the order presented in [Table 1](#) and will be annotated with the total population size relevant to that table/treatment, including any missing observations.

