Summaries of the frequency of influenza H3 HA-specific (M2SR-like and QIV-like viruses) and conserved internal viral protein-specific IFN- γ producing T-cells will include the mean (or geometric mean if data are log-normally distributed) and corresponding 95% confidence interval as well as the median, minimum, and maximum values. Fold rise from baseline will be summarized by arithmetic or Williams mean [4] if data are approximately normally or log-normally distributed, respectively, or median if data are not approximately normally distributed by inspection. Differences in frequency between the study groups will be presented. Differences in QIV-like strains will be calculated based on results to the year-matched strain. Sum Test, as appropriate. Summaries of IFN- γ producing T cells are presented in [Table 34](#), [Table 35](#), [Table 36](#), and [Table 37](#).

Figures depicting the GMT (HAI, MN, sIgA) or frequency (IFN- γ producing T cells) for each strain and assay over time will be presented beginning with [Figure 2](#) and continuing through [Figure 13](#) (GMTs), and [Figure 14](#), [Figure 15](#), [Figure 16](#), and [Figure 17](#) (frequencies).

Reverse cumulative distribution (RCD) plots will be presented for each assay (HAI, MN, and sIgA) and strain generated with separate panels for each visit, and separate curves within each panel for each study arm and overall. HAI and MN antibody titers for the M2SR-like and QIV-like A/H3N2 strains are shown beginning with [Figure 18](#) and continuing through [Figure 29](#).

The spearman correlation and corresponding p-value between strains for each assay (HAI, MN, relative and specific sIgA, and IFN- γ T cell responses) will be calculated at each time point within each study arm and

overall. The correlations will be depicted in scatter plots as [Figure 30](#), [Figure 31](#), [Figure 32](#), [Figure 33](#), [Figure 34](#), and [Figure 35](#).

The spearman correlation and corresponding p-value between HAI and MN antibody titers for each strain (M2SR-like and QIV-like A/H3N2 (within and between strains)) will be calculated at each time point within each study arm and overall. The correlation will be depicted in scatter plots in [Figure 36](#) and [Figure 37](#). The spearman correlation of T cell responses between peptides tested will be presented for each strain as shown in [Figure 38](#) and [Figure 39](#).

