8.3. Exploratory Immunogenicity Analyses

Completion of exploratory immunogenicity assays are contingent upon seeing scientifically relevant increased response in the M2SR-vaccinated group for the indicated assay, as determined by the scientific lead (SL) and principal investigator (PI) at the time of primary and secondary analyses.

HA ELISA reactivity with groups 1 and 2 HA stem domains of the viral hemagglutinin and serum anti-NA antibody titers to N1 and N2 neuraminidases measured by ELLA or ELISA will be completed if a scientifically relevant increase in rates of either seroconversion or 4-fold rise in either M2SR or QIV matched H3HA-specific HAI and/or MN assays in the M2SR vaccinated arm are observed after the H3N2 M2SR vaccination.

Anti-NA IgA responses to N1 and N2 neuraminidases will be assessed if a scientifically relevant increase in GMFR is observed for M2SR matched nasal sIgA is observed in the M2SR vaccinated arm after the H3N2 M2SR vaccination.

CD4⁺ and CD8⁺ T cell responses to the H3 HA present in the M2SR vaccine and pools of highly conserved Influenza A T cell epitopes will be assessed if a scientifically relevant increase in either H3 HA-specific or conserved peptide epitope-specific IFN- γ producing T cells is observed post M2SR vaccination for participants who received M2SR compared to participants who received placebo.

Planned analyses for any exploratory cellular immunology assays that are conducted based on the criteria above will be presented in an addendum to this SAP.

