	2-Fold Rise - % (95% CI)	xx (xx.x,xx.x)	xx (xx.x,xx.x)	xx (xx.x,xx.x)	xx (xx.x,xx.x)	xx (xx.x,xx.x)	xx (xx.x,xx.x)	xx (xx.x,xx.x)	xx (xx.x,xx.x)	xx (xx.x,xx.x)	xx (xx.x,xx.x)	xx (xx.x,xx.x)	xx (xx.x,xx.x)

Table 32: Summaries of Nasal sIgA Against QIV-like H3 HA by Time Point and Study Group - mITT Population (Continued)

Time Point	Statistic	Without Normalization						With Normalization					
		M2SR (N=X)			Placebo (N=X)			M2SR (N=X)			Placebo (N=X)		
		2018-2019 QIV	2019-2020 QIV	All QIV	2018-2019 QIV	2019-2020 QIV	All QIV	2018-2019 QIV	2019-2020 QIV	All QIV	2018-2019 QIV	2019-2020 QIV	All QIV
	4-Fold Rise - % (95% CI)	xx (xx.x,xx.x)	xx (xx.x,xx.x)	xx (xx.x,xx.x)	xx (xx.x,xx.x)	xx (xx.x,xx.x)	xx (xx.x,xx.x)	xx (xx.x,xx.x)	xx (xx.x,xx.x)	xx (xx.x,xx.x)	xx (xx.x,xx.x)	xx (xx.x,xx.x)	xx (xx.x,xx.x)

Note: N= Number of subjects in the Modified Intent-to-Treat Population; n = Number of subjects with results reported.

[Implementation Note: This table will be repeated for both the strain A/Singapore/INFIMH-16-0019/2016 (grown in eggs and missing HA glycosylation site) and A/NorthCarolina/04/2016 (grown only in cell lines and retains HA glycosylation site) and the corresponding 2019/2020 QIV strain(s). If strains do not change for the 2019/2020 seasonal QIV, display will be limited to the “All QIV” columns.]

Table with similar format:

Table 33: Summaries of Nasal sIgA Against QIV-like H3 HA by Time Point and Study Group - PP Population

Table 34: Summaries of IFN- γ T Cell Responses Against M2SR-like H3N2 by Peptide, Time Point and Study Group - mITT Population

[Implementation Note: This table will be repeated for all proteins/peptide pools tested.]

Time Point	Statistic	M2SR (N=X)	Placebo (N=X)
Baseline	n	x	x
	Mean Frequency (95% CI)	x.x (x.x,x.x)	x.x (x.x,x.x)
	Median Frequency [Min, Max]	xx [xx,xx]	xx [xx,xx]
Day 8	n	x	x
	Mean Frequency (95% CI)	x.x (x.x,x.x)	x.x (x.x,x.x)
	Median Frequency [Min, Max]	xx [xx,xx]	xx [xx,xx]
	Fold Rise (95% CI)	x.x (x.x,x.x)	x.x (x.x,x.x)
Day 22	n	x	x
	Mean Frequency (95% CI)	x.x (x.x,x.x)	x.x (x.x,x.x)
	Median Frequency [Min, Max]	xx [xx,xx]	xx [xx,xx]
	Fold Rise (95% CI)	x.x (x.x,x.x)	x.x (x.x,x.x)
Day 57	n	x	x
	Mean Frequency (95% CI)	x.x (x.x,x.x)	x.x (x.x,x.x)
	Median Frequency [Min, Max]	xx [xx,xx]	xx [xx,xx]
	Fold Rise (95% CI)	x.x (x.x,x.x)	x.x (x.x,x.x)
Day 93	n	x	x
	Mean Frequency (95% CI)	x.x (x.x,x.x)	x.x (x.x,x.x)
	Median Frequency [Min, Max]	xx [xx,xx]	xx [xx,xx]

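### The ELISPOT fold rise has no rule for a zero baseline, and the planned arithmetic or Williams mean of the ratios is not centred on 1 when nothing changes

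*SAP*

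**What the plan says.** SAP 3.3 gives HAI and neutralization a limit of detection of 10 and replaces lower values by 5. It gives nasal sIgA a limit of 2 and replaces lower values by 1. The ELISPOT sentence is different. It begins "The lower limit of detection for the frequency of conserved internal viral protein-specific" and ends by saying that the limit per million "peripheral blood mononuclear cells (PBMC) as measured by ELISPOT assay is 0". No replacement value follows, and H3 HA-specific cells are not mentioned.

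SAP 6.1 sets the general rule: "For post-baseline visits, fold rise from baseline will be calculated". For ELISPOT, SAP 8 says: "Fold rise from baseline will be summarized by arithmetic or Williams mean [4] if data are approximately normally or log-normally distributed, respectively". The same sentence adds a third branch, the median, when inspection shows that the data are not approximately normal. Tables 34–37 carry a fold-rise row with a 95% interval at each of five post-baseline visits, and no footnote covers a zero baseline. SAP 6.1 bases intervals for means on Student's t. SAP 6.5 rules out imputation of missing values.

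SAP 8.3 makes the CD4/CD8 T cell assays depend on whether a relevant increase in IFN-γ "producing T cells is observed post M2SR vaccination for participants who received M2SR compared to participants who received placebo". The scientific lead and the principal investigator judge this.

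The SAP disagrees with itself on where ELISPOT belongs. Section 4.1 lists it among assays that are run only if responses are seen, with analyses left to an addendum. Sections 3.2.2, 4.5.1 and 8 treat it as a secondary endpoint analysed in this SAP.

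**The concern.** A ratio to baseline needs a positive baseline. The serum and nasal assays have one by construction; ELISPOT does not. A child with no spots on Day 1 has an undefined or infinite fold rise at every later visit, and the programmer must then choose, with data in hand, whether to drop the child, set a floor or add an offset. These children have no detectable T cells before vaccination, so leaving them out changes whom the row describes.

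The second problem remains even without zeros. A summary of fold rise should read 1 when nothing has happened. An arithmetic mean of ratios, or a Williams mean of ratios, does not have this property, so a within-arm figure above 1 could be read as a response when it reflects only assay and day-to-day variation. ELISPOT is the only secondary endpoint for the cellular-response objective.

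**Working it through.** The documents give no ELISPOT fold-rise, spot-count or variability figure, so there is nothing of the plan's to reproduce. All spot means and SDs below are assumptions; n = 25 per arm is from SAP 5.

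**1. Zero baseline.** Let R = post/baseline. The half-limit rule gives 10/2 = 5 for HAI and neutralization and 2/2 = 1 for sIgA. For ELISPOT it would give 0/2 = 0, so R stays undefined. The Williams mean of ratios is W = exp(mean of log(1 + R)) − 1, which needs R first. If a share p0 of children have a zero baseline, 25 × p0 have no ratio, and the chance of at least one is 1 − (1 − p0)^25:

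| p0 | Children of 25 | P(at least one) |
|---|---|---|
| 5% | 1.25 | 0.72 |
| 10% | 2.5 | 0.93 |
| 20% | 5 | 0.996 |
| 30% | 7.5 | >0.99 |

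**2. No change, all counts positive.** Take one child who doubles and one who halves.
- Arithmetic: (2 + 0.5)/2 = 1.25.
- Williams: √(3 × 1.5) − 1 = 1.12.
- Geometric: √(2 × 0.5) = 1.00.

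In general, if baseline and post are exchangeable, R and 1/R have the same distribution. Then E[R] = ½E[R + 1/R] ≥ 1. Also E[log(1 + R)] = ½E[log(2 + R + 1/R)] ≥ ½ log 4 = log 2, so W ≥ 1.

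The plan assigns the Williams mean to log-normal data. With log R ~ N(0, s²), numerical integration gives W, and simulation of arms of 25 with a t interval on log(1 + R) gives the share whose lower 95% limit exceeds 1:

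| s | E[log(1 + R)] | W | Lower limit above 1 (nominal 2.5%) |
|---|---|---|---|
| 0.5 | 0.723 | 1.06 | 6% |
| 0.7 | 0.751 | 1.12 | 8% |
| 1.0 | 0.806 | 1.24 | 13% |

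The geometric mean of the same ratios is centred on 1.00, and its lower limit exceeds 1 in 2.5%.

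**3. No change, zero baselines dropped.** Assume independent Poisson counts with the same mean at both visits. The arithmetic mean is then E[post] × E[1/baseline, given baseline > 0]. At mean 1 this is 1 × 0.767 = 0.77.

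| Mean spots | Dropped of 25 | Arithmetic | Williams |
|---|---|---|---|
| 0.5 | 15.2 | 0.44 | 0.33 |
| 1 | 9.2 | 0.77 | 0.60 |
| 2 | 3.4 | 1.15 | 0.93 |
| 4 | 0.5 | 1.32 | 1.11 |

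Dropping zero baselines but keeping zero post values pulls the means down, while averaging ratios pushes them up. Which effect wins depends on the counts.

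**4. The median branch.** In the log-normal setting of step 2 the sample median averages 1.01 to 1.03 at n = 25. It still needs a ratio for each child, and at a Poisson mean of 1 with zero baselines dropped it is 0.5. SAP 6.1 states no interval method for it.

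**5. The proposed definition.** With (post + 1)/(baseline + 1), every child has a ratio. The log of the geometric mean estimates E[log(post + 1)] − E[log(baseline + 1)], which is 0 under no change, so the summary is centred on 1.00. A floor alone is not enough. With 0.5 spot substituted for zeros, across the overdispersed count scenarios tried, the arithmetic mean still reads 1.06 to 1.75 and the Williams mean 1.03 to 1.27.

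**The case against.** The strongest reply is that little rests on this row.

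- The endpoint is worded as a frequency. Protocol 11.4.3 promises descriptive frequency summaries, Tables 34–37 give the mean and median frequency with range at each visit, and Listing 10 gives individual values. This stands: the endpoint is not lost.
- A reader might infer that a spurious fold rise decides whether the CD4/CD8 assays are run. SAP 8.3 does not support that. It compares M2SR with placebo recipients and leaves the decision to judgement, and an error of similar size in both arms largely cancels.
- A reader might also infer that noise alone will show a rise in both arms. Step 3 shows that this fails at low counts. The larger figures from averaging log-normal ratios arithmetically (1.13, 1.28 and 1.64 at the same SDs) should not be quoted against the plan either, because for log-normal data it uses the Williams mean.
- The median branch covers skewed data. It deals with most of the centring problem when counts are well above zero, but not with zero baselines.
- SAP 4.1 defers ELISPOT to an addendum. That conflicts with SAP 3.2.2, 4.5.1 and 8, and SAP 6.2 and 8.3 speak of an addendum for exploratory measures. No zero rule appears in the documents supplied, so the definition is needed in either place.
- Williams mean may have been meant as a ratio of Williams means of the frequencies, which handles zeros and gives about 1.00 under no change. SAP 8 applies it to the fold rise itself; if the other reading was intended, the text should say so.

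The SAP also never says that zero-baseline children will be dropped. It says nothing, which is the gap.

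**Conclusion.** The point holds for the fold-rise rows of Tables 34–37. As written they cannot be computed for a child with a zero baseline, and the two planned means are not centred on 1 under no change. That the ratio is undefined, and that the means are at least 1 when all counts are positive and the two visits are exchangeable, follow from the definitions. The magnitudes do not: they rest on the assumed log SDs, Poisson means and shares of zero baselines. Once zeros are handled ad hoc, neither the size nor the direction of the error is controlled.

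This should be corrected before unblinding. It does not touch the primary safety objective or the frequency summaries, and it bears less on between-arm comparisons than on within-arm fold rises. The trial tests no formal hypothesis (Protocol 11.1), so the harm is a misleading descriptive figure.

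**What to change.** - **SAP 3.3:** define ELISPOT fold rise for all peptide pools, H3 HA included, as (post + c)/(baseline + c), applied to every child and visit. Fix c before unblinding, for example one spot expressed per million PBMC.
- **SAP 8 and Tables 34–37:** replace the arithmetic or Williams mean of ratios by the geometric mean of this ratio, with a t-based interval on the log scale. For frequencies that contain zeros, use a Williams mean in place of the geometric mean, which has no logarithm for 0. Add the change in spots per million.
- **SAP 4.1:** reconcile the contingent-assay and addendum wording with 3.2.2, 4.5.1 and 8, and carry the same definition into any addendum.

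The cost is a few lines of text and one derived variable, with no new samples. The downside is that fold rises from very low baselines shrink toward 1, sometimes noticeably: with c of one spot, a rise from 1 to 4 spots reads (4 + 1)/(1 + 1) = 2.5 instead of 4. The added change in spots per million shows what the ratio compresses.
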